8.3 BLINDING PROCEDURE

This study will be evaluator-blinded, so the PI or delegated evaluator conducting the NACDG grading evaluations will not know the placement of the TM and control patched test sites. The PI or delegated evaluator should not participate in product(s)/patch application and should not have access to the randomization.

In the event that the PI/evaluator believes an un-blinding is necessary and circumstances allow, the PI/designee will contact the Study Manager who will consult with the DPR to determine whether unblinding is needed. If it is determined that the blind should be broken, the PI/evaluator will contact the designated site representative to obtain information about the individual subject's randomization. The time, date, and reason for the un-blinding should be noted in the subject's source document and documentation should be provided to the Sponsor.

If there is a medical emergency and the PI/evaluator deems it necessary to know the randomization urgently for the subject's proper medical care, then the PI/evaluator may break the blind immediately by contacting the designated site representative. The PI/designee should promptly document and explain to the Study Manager any premature un-blinding.

The PI/evaluator may assist with data entry/review/analysis after individual subjects complete all test procedures. This will not be documented as premature un-blinding.

8.4 STUDY MATERIAL STORAGE AND ACCOUNTABILITY

The PI or designee must ensure that deliveries of test material(s) from the Sponsor are correctly received by a responsible person and that the test material(s) is stored in a secure area under recommended storage conditions. The test material(s) will be secured in a locked room or cabinet that is only accessible to authorized site personnel and kept at 59 - 86°F (15 -30°C). Temperature should be recorded at least daily. The PI must maintain adequate records documenting the receipt, use, loss, or other disposition of the investigational product on the Investigational Product Accountability/Dispensing Log or site equivalent

At the end of the study, investigational test material(s) (used and/or unused) may be destroyed by the site following its Standard Operating Procedure (SOP) and in compliance with applicable regulations, institutional policy, and any special instructions provided by the Sponsor, or they may be returned to the Sponsor depending on the product classification.

When product is destroyed on-site, the destruction must be properly documented and documentation provided to the Study Manager and/or designee.

In case of return to Sponsor, all containers must be returned to [REDACTED].

8.5 PRODUCT QUALITY COMPLAINTS

A Product Quality Complaint (PQC) is any written, electronic, or oral communication that alleges deficiencies related to the identity, quality, durability, reliability, or safety of a product, including its labeling, delivery system or packaging integrity. It also includes device malfunctions. Any PQC discovered during the initial inventory should follow the instructions provided on the receipt letter; no PQC form should be filed for issues identified when opening or unpacking a shipment. Subsequently, any observation of a PQC requires immediate notification to the Study Manager via a completed PQC form and telephone call. The PI or designee should complete, sign, and forward a copy of the PQC form to the Study Manager.

In addition, PQC information must be included on the Investigational Product accountability and reconciliation Form or equivalent in the comments field. The Study Manager listed can assist you or answer questions related to this process. To aid in the initial conversation and understanding of a PQC, the site staff may be asked to photograph the issue and send it to the Study Manager.

8.6 APPLICATION OF THE INVESTIGATIONAL PRODUCT

Test materials will be applied using occlusive or semi-occlusive patches. The patch type may be changed during the study if irritation develops. Occlusive patches consist of a non-woven cotton pad (e.g., Webril®) covered by Blenderm tape and held securely to skin on all sides with a porous, hypoallergenic tape (e.g., Micropore®). Semi-occlusive patches consist of a non-woven cotton pad (e.g., Webril®) covered and held securely to skin on all sides with a porous, hypoallergenic tape (e.g., Micropore®). Open patches consist of a non-woven cotton pad (e.g., Webril®) held to the skin on 2 opposing sides by a strip of hypoallergenic tape (e.g., Micropore®). The pad is open on 2 sides like a Band-Aid®.

Patches will be placed on the upper back, to the right and left of the spine. Patches will not be applied closer than 2 centimeters (cm) to each other. The cotton pads used for the patches are approximately 4 cm² in area, and will be dosed with a quantity of test material as follows (unless otherwise instructed by the Sponsor):

- Liquids and fragrances approximately 100 microliters (µL)
- Creams, lotions, petroleum, etc. approximately 100 µL
- Paper, powder or other solid materials a sufficient amount to cover the pad area

Patches will be applied starting at the lower edge of the patch and pressing from below to let air escape. The patch will be secured by gently rubbing the tape (especially the corners) to ensure good adherence.

9 INVESTIGATIONAL PLAN

9.1 STUDY PROCEDURES AND EVALUATION SCHEDULE

Pre-Study:

Candidate subjects will be recruited using IRB-approved materials. Interested candidates will be scheduled for Visit 1.

Screening/Baseline: Visit 1

Interested candidates will report to the site and take part in the following procedures:

1. Prospective candidates will be sequentially assigned a 2-digit screening number preceded by "S" (e.g. S01).
2. Subjects will be given an IRB-approved ICD and IRB-approved Supplemental Consent form (when applicable) to read and sign. They will have all of their study related questions answered by the Investigator or designated staff, and if they agree, they will sign 2 copies of the ICD and Supplemental Consent form (when applicable). They will retain 1 copy, and 1 will be kept in the study file.
3. Subjects will complete a health and eligibility questionnaire and a medical and medication history questionnaire.
4. Potential test sites (upper back) will be examined by the Investigator or designee for qualification criteria.
5. The screened subjects that meet all eligibility requirements will be enrolled into the study and assigned a subject number as describe in the "Randomization" section.
6. A delegated clinician will delineate up to six test sites on the subject's upper back, to the right and left of the spine, using an indelible marker. Each test site will be a 4 cm² and no closed than 2 cm² from each other. The test sites may be re-delineated at subsequent visits as needed
7. The test sites will be wiped with distilled or deionized water and allowed to air dry prior to patching.
8. The test material dosed patches and an undosed negative control patch will be applied to each subject's upper back according to the predetermined randomization.
9. Subjects will be provided with a calendar of study visits and study instructions. Subjects will be reminded of sun exposure/tanning and swimming/hot tub restrictions. Subjects will also be instructed to reinforce the edges of the patch with a bandage tape in the event that the tape applied in the clinic does not adhere.

Interim Visits: Visit 2 – Visit 12

Visit 2 will be completed 48-72 hours post Visit 1. Visits 3-12 will occur 48-72 hours post each subsequent visit, i.e., Monday, Wednesday, and Friday for four consecutive weeks. Subjects will report to the site at their scheduled visit time and will participate in the following procedures at each interim visit:

1. The PI or designee will interview the subjects to collect and record any AEs or changes to health/concomitant medications that may have occurred since the previous visit. Subjects will also be interviewed for compliance with study directions. Refer to Adverse Event Reporting section.
2. Patches applied during the prior visit will be removed by clinic personnel.
3. Each test site will be evaluated for irritation/reactions by the delegated evaluator.
4. Test sites may be re-delineated as needed, as described in Visit 1.

5. New test material dosed patches and an undosed negative control patch will be applied to the same test sites as described for Visit 1.

Make-up Visit

As necessary, a subject may complete a make-up patching visit. Make-up will be conducted 48-72 hours post Visit 12. Subject will return to site for Visit 13 for the collection of Follicular Biopsies. Subjects will report to the site at their scheduled visit time and will participate in the following procedures:

1. The PI or designee will interview the subjects to collect and record any AEs or changes to health/concomitant medications that may have occurred since the previous visit. Subjects will also be interviewed for compliance with study directions. Refer to Adverse Event Reporting section.
2. Patches applied during the prior visit will be removed by clinic personnel.
3. Each test site will be evaluated for irritation/reactions by the delegated evaluator.
4. Test sites may be re-delineated as needed, as described in Visit 1.
5. New test material dosed patches and an undosed negative control patch will be applied to the same test sites as described for Visit 1.

Visit 13:

Visit 13 will be conducted 48-72 hours post Visit 12. Subjects will report to the site at their scheduled visit time and will participate in the following procedures

1. The PI or designee will interview the subjects to collect and record any AEs or changes to health/concomitant medications that may have occurred since the previous visit. Subjects will also be interviewed for compliance with study directions. Refer to Adverse Event Reporting section.
2. Patches applied during the prior visit will be removed by clinic personnel.
3. Each test site will be evaluated for irritation/reactions by the delegated evaluator.
4. A delegated clinician will collect follicular biopsies from each test site as described below in the *Study Instrument(s)* section.
5. The PI or designee will interview the subjects to collect and assess any AEs or changes to health.
6. After all assessments are completed, subjects will leave site.

Note: 72-hour exposure time is only applicable for visits conducted on Friday and/or to allow for site closed days.

Site Irritation / Reaction Grading

At visits 2 through 13 (and makeup visit if applicable), the designated test sites will be graded for irritation/reactions using the North American Contact Dermatitis Group (NACDG) grading scale. Sites will be adequately illuminated using lighting provided by a 60-watt incandescent blue day light bulb.

NACDG Grading Scale

- 0 No reaction
- +0.5 Macular erythema
- +1 Indurated erythema
- +2 Erythema, infiltration and vesicles
- +3 Bullous reaction or ulcer

If irritation develops as indicated by the NACDG score, the patch type may be changed or patch applications may be skipped for specific sites. Skipping a patch application should be documented as a protocol deviation. This may also have an impact on the follicular biopsy process at the final study visit. Any changes made to the patch type, application schedule, or biopsy procedures will be documented in the appropriate source documents.

9.2 STUDY INSTRUMENT(S)

Follicular Biopsies:

Follicular biopsies will be collected from each patch site at Visit 13 or make-up visit for each subject. The following procedures will be followed for follicular biopsy collection:

- The test sites will be gently cleansed with warm soapy, water and patted dry.
- A glass slide containing a drop of cyanoacrylate glue will be held against each site until it has dried.
- The slide will then be removed slowly, so as to extract follicles and their contents.
- The specimen slides will be stored in labeled slide boxes until graded.
- The specimens collected using the cyanoacrylate follicular biopsy technique will be evaluated by a trained grader using a stereomicroscope (magnification ratio of 0.8). Hyperkeratotic follicles (microcomedones) will appear as cylindrical horny impactions surrounding extracted vellus hairs.

Specimens will be graded using a 5-point global assessment scale as follows:

- 0 None (0%, No microcomedones)
- 0.5 Slight (1-24% Smallish horny masses)
- 1 Mild (25-49% Smallish horny masses)
- 2 Moderate (50-74% Moderately sized horny masses)
- 3 Severe (75-100% Larger globoid microcomedones)

The results from the microcomedone grading of the follicular biopsies will be recorded using the Stephens Electronic Data Capture (EDC) system, if available, which documents the identity of the evaluator/technician as well as the time and date of all entries, or all corrected entries. Subject data can also be provided by Stephens at the Sponsor's request. Paper grading forms will be completed if EDC is unavailable. Any test site with a NACDG grading score of 2 or greater may not receive a follicular biopsy, which will be noted in the appropriate source documents.

9.3 SUBJECT COMPLETION/WITHDRAWAL

9.3.1 Subject Completion

Subjects are considered to have completed the study when all study procedures have been completed as designated by the protocol. Completion should be noted in the source documents and Screening and Enrollment log.

9.3.2 Subject Withdrawal

When an individual who has signed the ICD is not enrolled in the study or withdraws/is withdrawn prior to completing the study, the reason is to be documented in the source documents, Screening and Enrollment log, and in the final study report. Reasons for subject withdrawal may include:

- Screen Failure (e.g. fails to meet inclusion/exclusion criteria, chooses not to enroll, etc.)
- Participant is determined to be ineligible after enrollment
- Subject's choice to withdraw
- Investigator terminated (e.g. noncompliance, etc.)
- Adverse Event / SAE (must be reported in accordance with the reporting requirements defined in the Adverse Event Reporting Section.)
- Lost to follow-up
- Other

Subjects may withdraw from the trial at any time at their request, or they may be withdrawn at any time at the discretion of the Sponsor, PI, or designee for safety, behavioral, or administrative reasons. If a subject does not return for a scheduled visit, 3 documented attempts will be made to contact the subject in order to establish the reason for withdrawal, and the outcome will be documented. The PI or designee should inquire about the reason for withdrawal, request that the subject return for a final visit, if applicable, and follow-up with the subject regarding any unresolved adverse events.

Should a subject withdraw from the trial and also withdraw consent for disclosure of future information, no further evaluations should be performed and no additional data should be collected. The PI and staff may retain and continue to use any data collected before such withdrawal of consent.

Additional subjects may be enrolled in a test panel to compensate for early subject withdrawal

10 STATISTICAL ANALYSIS PLAN.

The per-protocol (PP) population will be the primary population for comedogenicity analyses. The PP population will include all subjects who received treatment and completed the study in general accordance with the protocol. Only the data of completing subjects will be analyzed. Subjects may be removed from the analysis in the case of an AE, SAE, non-compliance, or Investigator discretion. The reason for any subjects excluded from the analyses will be documented in a note to file and included in the study report.

Demographic data and baseline characteristics will be summarized for all subjects who are enrolled in the study. For continuous variables, descriptive statistics including number of subjects (N), mean, median, standard deviation (SD), minimum (MIN) and maximum (MAX) values will be presented. For categorical variables, the frequency and percentage of each category will be provided.

A descriptive statistical summary will be provided for the global assessments of microcomedone data from biopsies for the test material and control sites. The descriptive statistical summary includes the number of observations (N), mean, median, standard deviation (SD), minimum (MIN), and maximum

(MAX).

In addition, microcomedone scores will be analyzed using a mixed-effects model, where the test Material/negative control is a fixed effect and the subject is a random effect. Each test product will be compared to the negative control within the model frame. A test material will be considered positive for comedogenicity if it has a mean microcomedone value of 1.0 or greater, and is statistically greater than the mean microcomedone value for the negative control site.

All statistical tests will be 2-sided at significance level $\alpha=0.05$. P-values will be reported to 3 decimal places (0.000). No multiple testing corrections will be considered in the study. Statistical analyses are performed using SAS software version 9.30 or later series (SAS Statistical Institute). The results will be sent to the Sponsor along the raw data in a Microsoft Excel document at the completion of the study.

A test material is considered negative for comedogenicity as long as it satisfies 1 of the following 2 conditions: the microcomedone mean score is less than 1.0 and/or the mean score is not greater than the control with p-value < 0.05 .

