considered clinical endpoints if they are mild in nature and should not be reported as AE. These conditions may or may not resolve over time. Symptoms that are persistent and moderate to severe in nature, or that involve elevation (e.g. edema, papules, vesicles, spreading) will be considered adverse events (AEs). The Investigator or designee will have the final authorization to determine if a reaction will be considered an AE.

If a subject is discontinued due to worsening of a sign or symptom (including worsening of the signs and or symptoms recorded as part of the evaluations), then it should be recorded as an AE.

Treatment Emergent AE (TEAE)

TEAE is defined as any event not present prior to the initiation of the IPs. Note that AEs will be summarized for all subjects who signed the ICD, differentiating TEAEs.

AEs are considered serious and require expedited reporting if they meet the definition of a **Serious Adverse Event** (see part below).

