11.3.3 Procedures for Reporting Adverse Events

All AEs will be reported from the time a signed and dated ICD is obtained until completion of the subject’s last study procedure or visit (or termination if the subject terminates early from the study for any reason).

AEs that occur between end of study and 30 calendar days after completion of the study will only be reported to the Sponsor if they are serious. SAEs are reportable beyond this period if the event is considered study-related. The Sponsor will evaluate any safety information that is spontaneously reported by the PI beyond the time frame specified in the protocol.

Subjects are encouraged to report AEs spontaneously and in response to questioning during the visit (e.g. if they have had any side effects/issues or changes in their health). For each AE reported by the subject or observed by the study team, the study team member should notify the PI, Study Physician, or designee, who will collect information about the event.

All AEs, regardless of seriousness, severity, or presumed relationship to study procedures, must be recorded using medical terminology on the Sponsor provided AE form and then entered into the Electronic Data Capture (EDC), Medidata Rave AE Universal Database. These events must then be entered into the Medidata Rave AE Universal Database within 5 business days of the site’s awareness. The DPR review of AEs/SAEs in Medidata Rave AE Universal Database will be conducted within 5 business days of each entry into Medidata Rave AE Universal Database in order to escalate any potential safety signal to the Department Head.

Whenever possible, diagnoses should be given when signs and symptoms are due to a common etiology (e.g., cough, runny nose, sneezing, sore throat, and head congestion should be reported as “upper respiratory infection”). The PI or, if the PI does not have a medical background, a medically qualified individual (MD/DO) designee, must record or confirm their opinion concerning the

seriousness, severity, and relationship of the AE to the study. All measures required for AE management must be recorded and reported according to Sponsor instructions.

The PI or designee must also report AEs to the appropriate IRB unless otherwise required and documented by the IRB.

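### Section 10 allows removals from the only comedogenicity analysis for an AE, SAE, non-compliance or at Investigator discretion, with no blinded cut-off and no second analysis set to show their effect

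*Combined protocol and SAP*

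**What the plan says.** Section 10 sets the population: "The per-protocol (PP) population will be the primary population for comedogenicity analyses". That population is all treated subjects who finished in general accordance with the protocol, and no list of qualifying deviations is given. Two further sentences narrow it: "Only the data of completing subjects will be analyzed", and then "Subjects may be removed from the analysis in the case of an AE, SAE, non-compliance, or Investigator discretion". The removal sentence sets no condition on severity, relatedness or timing. The reason for each exclusion goes into a note to file and the study report. No other comedogenicity population and no sensitivity analysis is defined.

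The verdict has two parts. "A test material will be considered positive for comedogenicity if it has a mean microcomedone value of 1.0 or greater", and it must also be statistically greater than the negative control. Failing either part makes the material negative.

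Section 8.3 keeps the irritation evaluator away from the randomization, but adds: "The PI/evaluator may assist with data entry/review/analysis after individual subjects complete all test procedures". It says this will not be recorded as premature unblinding.

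Section 11.3.2.1 decides which reactions count as AEs. Listed skin signs and symptoms are "considered clinical endpoints if they are mild in nature and should not be reported as AE". By contrast, "Symptoms that are persistent and moderate to severe in nature, or that involve elevation" are AEs, and the Investigator or designee has the final say.

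**The concern.** A reaction serious enough to count as an AE can be caused by the product. If it is also a ground for removing the subject, membership of the analysis can depend on the product's effect. Removal takes the whole subject, so the control site and any other product's sites go too (Section 9.1 allows up to six). That keeps the within-subject comparison paired, but it does not protect the absolute criterion of a mean of 1.0.

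The decision is also undated. The person with removal discretion is the Investigator, and Section 8.3 allows the PI/evaluator into data review and analysis as each subject finishes. The plan does not say that exclusions are settled by then.

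Section 2 says the panels are run on products claiming to be non-comedogenic. If a negative result depended on who was removed, the report would list the reasons but would not have to show the effect.

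**Working it through.** **Plan's own figure.** Section 7 enrols up to 18 to obtain 15 completers. It gives no power, effect size, SD or dropout rate, so the figure cannot be re-derived. It leaves a margin of 18 − 15 = 3 subjects. That is not a cap on removals: Section 9.3.2 allows extra enrolment to make up for early withdrawal, and nothing limits exclusions.

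**Inputs from the documents.** Grades 0, 0.5, 1, 2, 3 (Section 9.2); cut-off 1.0, two-sided 0.05 (Section 10); N = 18 (Section 7).

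**Step 1: the cut-off.** Remove k of 18, with retained mean m and removed grades averaging g. The full mean is [(18 − k)m + kg]/18. At m = 1.0, with g from 0 to 3:

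- k = 1: 17/18 = 0.94 to 20/18 = 1.11
- k = 2: 16/18 = 0.89 to 22/18 = 1.22
- k = 3: 15/18 = 0.83 to 24/18 = 1.33

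**Step 2: when the mean part can change sides.** A retained mean below 1.0 can belong to a full mean of 1.0 or more only if m ≥ (18 − 3k)/(18 − k). A retained mean of 1.0 or more can belong to a full mean below 1.0 only if m < 18/(18 − k).

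- k = 1: m from 0.88 to below 1.06
- k = 2: m from 0.75 to below 1.125
- k = 3: m from 0.60 to below 1.20

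Outside these ranges, removals cannot alter the mean part. They can still alter the p-value.

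**Step 3: how special the removals must be.** Take an invented panel of 18 with product grades 3×0, 4×0.5, 5×1, 4×2, 2×3. The sum is 21 and the mean 1.17. No single removal brings it below 1.0, since (21 − 3)/17 = 1.06. Of the 153 possible pairs, one does: the two grade-3 subjects, giving 15/16 = 0.94. Of the 816 triples, 25 do (3.1%). In a panel like this a reversal needs selective removal; arbitrary losses rarely produce one.

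**Step 4: irritation-dependent removal, on assumed grades.** The documents give no grade distribution, reaction rate or link between irritation and grade, so all of these are assumptions. Product grades 0/0.5/1/2/3 have probabilities 0.12/0.22/0.28/0.26/0.12 (mean 1.27). Control grades have 0.40/0.35/0.18/0.06/0.01 (mean 0.51). The latent product–control correlation is 0.4. There are 60,000 panels of 18, judged by a paired t-test plus the mean rule. The k most irritated subjects are removed and compared with k removed at random, so that lost sample size is not counted as bias. The ranges cover irritation–control correlations of 0 and 0.4 times the irritation–product correlation r.

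| Removed | Random | r = −0.5 | r = −0.3 | r = +0.3 | r = +0.5 |
|---|---|---|---|---|---|
| 1 | 15% | 11–12% | 12–13% | 17–18% | 19–20% |
| 3 | 19% | 8–10% | 12–13% | 27–28% | 33–35% |

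Entries are the probability of a negative verdict; with no removal it is 13%. The paired t-test stands in for the planned mixed model with one product and one control on complete pairs, so panels with more sites are not covered. The table shows what removing reactors could do. It would be the same if the exclusion list were signed blind, so it does not measure the effect of deciding late.

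**The case against.** The removal reasons closely follow the withdrawal reasons in Section 9.3.2, and the sentence comes directly after the one restricting analysis to completers. It may do little more than restate that withdrawn subjects are not analysed, and most of those would have no biopsy anyway. That reading is fair. The wording still does not exclude the wider one, and a SAP should not leave the choice open.

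There are real safeguards. Exclusion reasons are reported. The irritation evaluator should not see the randomization, and microcomedones are read by a trained grader (Section 9.2). Deviations, which include skipped patches, go to the Study Manager and into the final report (Section 11.2). AEs are entered within five business days (Section 11.3.3), so a reaction during patching would normally be classified before the biopsy. The Sponsor receives the raw data and might recompute, although whether excluded subjects are in that file is not stated. Each of these helps. None fixes when exclusions are decided, and none requires the result with the removed subjects restored.

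A reader might infer that the Investigator will see assignment and grades and then choose whom to drop, or that the rule favours a negative verdict. The documents support neither. No passage says the Investigator has the grades when exclusions are decided, and no passage links irritation to microcomedone grade, so the bias could run either way. Nor should the rule be read as removing every reactor: it permits removal without requiring it, and mild reactions are not AEs.

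**Conclusion.** The point holds as a gap in the analysis rules. Section 10 permits outcome-related removals from the only defined comedogenicity analysis, sets no blinded cut-off for deciding them, and provides no analysis that would show their effect. This rests on the text alone and is secure.

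Its practical size is not known. The ranges in Steps 1 and 2 need only the grade scale and N = 18; they are limits on what removals could do. The percentages in Step 4 rest on assumed grades and correlations with a product mean near the cut-off. One removal has a small effect there. Three have a larger one, in a direction set by a correlation that the documents do not give. No bias is demonstrated. This is a cheap improvement.

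**What to change.** In Section 10, keeping per-protocol primary:

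1. Delete AE, SAE and unspecified Investigator discretion as reasons to drop a graded biopsy. Allow exclusion only for listed eligibility or compliance deviations that affect exposure or assessment. State how the analysis treats sites with irritation-driven skipped or changed patches. Section 9.1 logs skips as deviations, so reaction-dependent removal could otherwise return by that route.
2. Sign the exclusion list before those deciding have the assignment or the microcomedone grades, for example while the slides are stored ungraded (Section 9.2). Report any later change.
3. Add a sensitivity analysis of all treated subjects, using every graded site in the same mixed model. Report the two-part verdict under both sets and state any disagreement.
4. Report exclusions, withdrawals and unbiopsied sites by material, with reasons. Reconcile Sections 9.2, 9.3.1 and 10: a site with an NACDG score of 2 or more may go without biopsy, yet completion requires all procedures, so it is unclear whether such a subject is a completer. A tipping-point analysis of missing grades is optional.

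The cost is SAP wording, one signed list and some extra analysis and tabulation per panel, on data already collected. The drawback is that the all-graded set may include poorly exposed sites, which dilute the difference towards a negative verdict. Under the Step 4 assumptions, if 3 of 18 product sites scored like control, the probability of a negative verdict would be about 31% with all graded sites and 19% with those subjects removed. That is why it should remain a sensitivity analysis.
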